1.6. Summary

1.6.1. Study Rationale

This multicenter, placebo controlled study will be the first determination of safety and efficacy of PF-06651600 in subjects with moderate to severe active RA who have had an inadequate response to methotrexate (up to approximately 50% of subjects may also have had an inadequate response to 1 anti-TNF α biologic DMARD).

[figure not shown]
The subject population in this study is methotrexate non-responders. These subjects could potentially also have failed one TNF α inhibitor. The inclusion of subjects who have failed one TNF α inhibitor is driven by the fact that anti-TNF α therapy is widely used in the US (which is planned to be one of the countries participating in this study) in subjects who have failed methotrexate. The decision to limit the number of TNF α non responders in B7981006 (up to 50% of study subjects) is based on the American College of Rheumatology (ACR) recommendations to reserve anti-TNF α agents for RA subjects for whom prior methotrexate monotherapy led to an inadequate response, RA subjects with moderate disease activity and features of a poor prognosis, and for RA subjects with high disease activity, irrespective of prognostic features.¹⁵

In addition, although anti-TNF α therapy is very effective in controlling disease activity and slowing down radiological damage, prolonged response is only seen in approximately 60-70% of the subjects,⁷ which indicates that there is an un-met need for RA subjects who fail anti-TNF α therapy.

An 8 week study was determined of an appropriate duration to assess disease activity and provide safety information for PF-06651600 in subjects with RA. SDAI was selected as the primary endpoint since this assessment is the best predictor for transformational efficacy defined in terms of 6 month SDAI remission rate.

1.6.2. Dose Rationale

The dose selection strategy was designed to balance pharmacology and safety for an 8 week study) in this subject population.

The predicted PK parameters for PF-06651600 based on simulations using the global PK model are provided in Table 4.

Table 4. Summary of Predicted Steady State Plasma Pharmacokinetic and Pharmacodynamic Parameters Following Multiple Dose Administration of PF-06651600

Dose mg QD	C _{max} ng/mL	Predicted Margins ^a	AUC _{tau} ng.hr/mL	Predicted Margins ^a	IP-10 %CFB
200	1254 (2.1)	11	3712 (14)	14	42 (19)

AUC_{tau} = Area under the concentration-time curve from zero to 24 hours postdose at steady state; C_{max} = Peak plasma concentration; QD = Once daily; %CFB= percent change from baseline; human unbound fraction (fu) = 0.86; 1 ng/mL= 3.504 nM.

a. NOAEL-highest dose in dogs, 45 mg/kg/day; Week 8 mean male and female C_{max} (free) = 12,000 ng/mL; C_{max} (total) = 14,634 ng/mL; AUC_{tau} (free) = 44,100 ng•h/mL; AUC_{tau} (total) = 53,780 ng•h/mL. dog (fu) = 0.82.

The predicted exposure during the treatment period at a dose of 200 mg QD for 8 weeks is projected to maintain 12- and 14-fold safety margins for C_{max} and AUC_{tau}, respectively. The selective inhibition of JAK3 will lead to modulation of γ -common chain cytokine pathways, such as IL-7, IL-15 and IL-21 which have been implicated in the pathophysiology of RA. In lymphocytes, PF-06651600 inhibited JAK1/JAK3 dependent STAT5 and STAT3 phosphorylation by IL-15 and IL-21 respectively, with IC₅₀s of 56.5 ng/mL and 103 ng/mL, respectively. All other pathways were inhibited at IC₅₀s >5708 ng/mL. The predicted average percent IL-15 and IL-21 in-vitro signaling inhibition in human whole blood based on human PK are provided in Table 5.

Table 5. Summary of the Predicted Average Percent In Vitro Signaling Inhibition Based on Steady State PK from 200 mg PF-06651600

Cytokine	Average Percent Signaling Inhibition
	200 mg
IL-15	81
IL-21	71

Pharmacological modulation of the target can be inferred from the results.

1.6.3. Summary of Benefits and Risks

Overall, the safety profile observed during the Phase I program for PF-06651600 appears to be acceptable at dosages CCI administered orally.

Additional information for this compound may be found in the single reference safety document (SRSD), which for this study is the Investigator's Brochure.

1.6.4. Additional Information

Banked biospecimens will be collected for the purpose of conducting research; specific uses are described in the Banked Biospecimens section. Comparing the deoxyribonucleic acid (DNA), ribonucleic acid (RNA), protein, and metabolite variation patterns of subjects who respond well and those who respond poorly to treatment may help to better define the most appropriate group of subjects in which to target a given treatment. Collecting biospecimens for exploratory pharmacogenomic/genomic/biomarker analyses and retaining them in the Biospecimen Banking System (BBS) make it possible to better understand the investigational product's mechanism of action and to seek explanations for differences in, for example, exposure, tolerability, safety, and/or efficacy not anticipated prior to the beginning of the study.

Banked biospecimens retained in the BBS also can be used in research on diseases of inflammation.

Providing these biospecimens is a required study activity for study sites and subjects, unless prohibited by local regulations or ethics committee (EC) decision.

2. STUDY OBJECTIVES AND ENDPOINTS

[figure not shown]
Primary Objectives:	Primary Endpoints:

To evaluate the efficacy of PF-06651600 at 8 weeks in subjects with moderate to severe active RA.	
Change from baseline in simple disease activity index (SDAI) at Week 8.
Secondary Objectives:	Secondary Endpoints:

To evaluate the safety of PF-06651600.	
Safety and tolerability of PF-06651600 versus placebo; vital signs, laboratory tests, adverse events (AEs) including infections, and Serious Adverse Events (SAEs).

To assess other signs of clinical efficacy over 8 weeks.	
Change from baseline in SDAI at Weeks 1, 2, 4 and 6.Change from baseline in SDAI low disease activity scale (LDAS) and remission rates at Week 4, Week 6 and Week 8Change from baseline in DAS28 LDAS and remission rates at Week 4, Week 6 and Week 8. 
The following will also be calculated at Weeks 1, 2,4, 6 and 8:

	
• Change from baseline in DAS28-3 (ESR), DAS28-3 (CRP), DAS28 -4 (ESR), and DAS28-4 (CRP).• Change from baseline in hsCRP.• Change from baseline in the Tender/Painful and Swollen Joint Count (28).• Change from baseline in the Physician's Global Assessment of Arthritis.

• To assess the effect of PF-06651600 on patient reported outcome measurements.	
• Change from baseline in the Patient's Assessment of Arthritis Pain (VAS) and Patient's Global Assessment of Arthritis (VAS) at Weeks 1, 2, 4, 6 and 8.• Change from baseline in the HAQ-DI at Weeks 1, 2, 4, 6 and 8.
CCI	

• [Redacted]• [Redacted]• [Redacted]• [Redacted]• [Redacted]	
• [Redacted]• [Redacted]• [Redacted]• [Redacted]• [Redacted]

[Redacted]

3. STUDY DESIGN

Figure 1. Study Design Schematic

Note: N indicates the total number of completers.

This is a Phase 2a, 8 week randomized double-blind, parallel group, placebo controlled, multi-center study to assess the efficacy and safety profile of PF-06651600 in seropositive subjects with moderate to severe active rheumatoid arthritis with an inadequate response to methotrexate (up to approximately 50% of subjects may also have had an inadequate response to 1 anti-TNF α biologic DMARD).

Up to approximately 60 subjects may be randomized globally into the study to ensure at least approximately 50 subjects complete 8 weeks of active dosing (assuming a dropout rate of approximately 15%). Subjects will participate in this study for approximately 17 weeks. This includes an up to 5-week screening period, an 8 week treatment period, and a 4 week follow-up period.

After an up to 5 week screening period, eligible subjects will be randomized to receive 200 mg QD of PF-06651600 or placebo (matching tablets for PF-06651600 QD) every day for 8 weeks in a blinded fashion.

Subjects will remain on stable background arthritis therapy, which must include methotrexate (supplemented with folic/folinic acid per local treatment guidelines). Subjects additionally may continue stable doses of Nonsteroidal Anti-inflammatory Drugs (NSAIDs), COX-2 inhibitors, allowed opioids (at doses \leq the potency equivalent of 30 mg of orally-administered morphine), acetaminophen/paracetamol for pain control (\leq 2.6 grams per day), and/or low dose oral corticosteroids (\leq 10 mg prednisone or equivalent per day). Methotrexate must have been dosed orally for at least 3 months, the dose must have been stable for at least 4 weeks before first dose of study drug, and the dose must remain stable during the study. Allowed methotrexate doses are 15 to 25 mg, inclusive, weekly, unless there is documented (in the source documentation) intolerance to or toxicity from these doses, in which case a dose between 10 and <15 mg, inclusive, may be used.

Folic or folinic acid must be dosed per local standards of care stably for at least 4 weeks before first dose of study drug. NSAIDs, COX-2 inhibitors, allowed opioids and/or low dose oral corticosteroids (≤ 10 mg prednisone or equivalent per day) must be dosed stably for at least 4 weeks prior to first dose of study drug (See [Section 5.8](#)).

4. SUBJECT ELIGIBILITY CRITERIA

This study can fulfill its objectives only if appropriate subjects are enrolled. The following eligibility criteria are designed to select subjects for whom participation in the study is considered appropriate. All relevant medical and nonmedical conditions should be taken into consideration when deciding whether a particular subject is suitable for this protocol.

Subject eligibility should be reviewed and documented by an appropriate member of the investigator's study team before subjects are included in the study.

4.1. Inclusion Criteria

Subjects must meet all of the following inclusion criteria to be eligible for enrollment into the study.

1. Evidence of a personally signed and dated informed consent document indicating that the subject [or a legally acceptable representative] has been informed of all pertinent aspects of the study.
2. Willing and able to comply with scheduled visits, treatment plan, laboratory tests and other study procedures.
3. Male and female subjects (including Women of Childbearing Potential (WOCBP)) between the ages of 18 and 75 years, inclusive. For subjects >70 years old, the site must discuss subject eligibility with the study team to ensure that these subjects are sufficiently healthy to participate.
4. Female subjects of childbearing potential must test negative for pregnancy at screening visit and baseline visit.
5. Female subjects of nonchildbearing potential must meet at least 1 of the following criteria:
 - a. Achieved postmenopausal status, defined as follows: cessation of regular menses for at least 12 consecutive months with no alternative pathological or physiological cause and have a serum follicle-stimulating hormone (FSH) level confirming the postmenopausal state;
 - b. Have undergone a documented hysterectomy and/or bilateral oophorectomy;
 - c. Have medically confirmed ovarian failure.

All other female subjects (including female subjects with tubal ligations) are considered to be of childbearing potential.

6. Diagnosis of rheumatoid arthritis (RA) and meeting the 2010 American College of Rheumatology (ACR)/European League Against Rheumatism (EULAR) classification criteria (see [Appendix 2](#)) for RA with a Total Score $\geq 6/10$. The duration of time since diagnosis of RA should minimally be sufficient to meet the definition of methotrexate inadequate response (see criteria 10 below).
7. Meets Class I, II or III of the ACR 1991 Revised Criteria for the classification of Global Functional Status in RA (see [Appendix 2](#)).
8. The subject has active disease at both Screening and Baseline, as defined by both:
 - ≥ 6 joints tender or painful on motion; AND
 - ≥ 6 joints swollen;

and

 - High sensitivity C reactive protein (hsCRP) ≥ 7 mg/L at screening performed by the central laboratory. Subjects who do not meet this entry criterion but satisfy all other study entry criteria may have serum hsCRP concentration re-tested and, if the repeat hsCRP concentration is ≥ 7 mg/L prior to the baseline visit, will be eligible to enroll into the study provided all other inclusion/exclusion criteria are met.
9. Subjects must be seropositive (rheumatoid factor positive and/or anti-citrullinated protein antibody positive) at the screening visit.
10. Subjects must have been taking oral MTX for at least 3 months at an adequate dose to determine that the subject had an inadequate response to MTX, defined, for the purpose of this study, by the investigator's and subject's opinions that the subject did not experience adequate benefit from methotrexate plus the presence of sufficient residual disease activity to meet the entry criteria. Allowed methotrexate doses are 15 to 25 mg, inclusive, weekly, unless there is documented (in the source documentation) intolerance to or toxicity from these doses, in which case a dose between 10 and <15 mg, inclusive, may be used (See [Section 5.8](#)). The dose must have been stable for at least 4 weeks before first dose of study drug, and the dose must remain stable during the study.
 - Subjects should be on an adequate and stable dose of folic acid (not less than 5 mg weekly, unless higher doses would violate the local label) for at least 4 weeks prior to the first dose of investigational product or oral folinic acid (≥ 5 mg once per week) supplementation for at least 4 weeks prior to the first dose of study drug. Folic acid must be dosed per local standards of care stably for at

least 4 weeks before first study dose and the dose must remain stable during the study. In countries which do not have approved folic acid 1 mg or folinic acid 5 mg presentations, a regimen of folic acid of at least ≥ 5 mg weekly is acceptable.

11. Up to 50% of subjects may have received one approved TNF α -inhibiting biologic agent administered in accordance with its labeling recommendations that was inadequately effective and/or not tolerated. For the purpose of this study, inadequate efficacy is defined by the investigator's and subject's opinions that the subject did not experience adequate benefit from the anti-TNF α inhibitor and the presence of sufficient residual disease activity to meet the entry criteria. The anti-TNF α inhibitor should have been discontinued for a minimum of the washout period defined as follows:

- etanercept (Enbrel[®]): 4 weeks.
- infliximab (Remicade[®]), adalimumab (Humira[®]), golimumab (Simponi[®]), certolizumab (Cimzia[®]): 10 weeks.

12. Subjects receiving non-prohibited medications (See [Section 5.8](#)) for any reason must be on a stable regimen, which is defined as not starting a new drug or changing dosage within 7 days or 5 half-lives (whichever is longer) prior to first study dose and the dose must remain stable during the study.

4.2. Exclusion Criteria

Subjects with any of the following characteristics/conditions will not be included in the study:

1. Investigator site staff members directly involved in the conduct of the study and their family members, site staff members otherwise supervised by the investigator, or subjects who are Pfizer employees, including their family members, directly involved in the conduct of the study.
2. Participation in other studies involving investigational drug(s) within 30 days or 5 half-lives (whichever is longer) prior to study entry (screening visit) and/or during study participation.
3. Other acute or chronic medical or psychiatric condition including recent (within the past year) or active suicidal ideation or behavior or laboratory abnormality that may increase the risk associated with study participation or investigational product administration or may interfere with the interpretation of study results and, in the judgment of the investigator, would make the subject inappropriate for entry into this study.

4. Any major illness/condition(s) or evidence of an unstable clinical condition (eg, renal, hepatic, hematologic, gastrointestinal, endocrine, pulmonary or local active infection/infectious illness) that, in the investigator's judgment will substantially increase the risk to the subject if he or she participates in the study.
5. Acute coronary syndrome (eg, myocardial infarction, unstable angina pectoris) and any history of cerebrovascular disease within 24 weeks before screening or in the period between the Screening Visit and the Baseline Visit.
6. Subjects with a known immunodeficiency disorder or a first degree relative with a hereditary immunodeficiency.
7. Subjects with acute or active chronic dermatological disorders within 4 weeks prior to study entry or in the period between the Screening Visit and the Baseline Visit.
8. Pregnant female subjects; breastfeeding female subjects; fertile male subjects and female subjects of childbearing potential who wish to become pregnant or who are unwilling or unable to use 2 highly effective methods of contraception as outlined in this protocol for the duration of the study and for at least 28 days after the last dose of investigational product.
9. History of alcohol or drug abuse with less than 6 months of abstinence prior to the Baseline Visit.
10. Subjects with any of the following acute or chronic infections or infections history:
 - a. Any infection requiring treatment within 2 weeks prior to the Screening Visit or in the period between the Screening Visit and the Baseline Visit.
 - b. Any infection requiring hospitalization, parenteral antimicrobial therapy within 60 days of the Baseline Visit, or as otherwise judged to be an opportunistic infection or clinically significant by the investigator, within the past 6 months of the Baseline Visit.
 - c. Known active or history of recurrent bacterial, viral, fungal, mycobacterial or other infections.
 - d. Recurrent (more than one episode) herpes zoster or disseminated (a single episode) herpes zoster or disseminated (a single episode) herpes simplex.
 - e. Infected joint prosthesis at any time with the prosthesis still in situ.
 - f. Subjects will be screened for Human Immunodeficiency Virus (HIV). Subjects who test positive for HIV will be excluded from the study.

- g. Subjects will be screened for hepatitis B virus infection and will be excluded if positive for hepatitis B surface antigen (HBsAg). Subjects with HBsAg negative testing but who test positive for hepatitis B core antibody (HBcAb) must have further testing for hepatitis B surface antibody (HBsAb). If HBsAb is positive, the subject will be excluded from the study.
 - h. Subjects will be screened for hepatitis C virus (HCV Ab). Subjects with positive HCV Ab tests will be reflex tested for HCV ribonucleic acid (HCV RNA). Only subjects with negative HCV Ab or HCV RNA will be allowed to enroll in the study.
11. Subjects treated with prohibited medications will be excluded unless appropriate washout has been performed (See [Section 5.8](#)).
12. Any current evidence of untreated latent or active TB infection, evidence of currently active TB by chest x-ray, residing with or frequent close contact with individual(s) with active TB. Subjects who have a positive Mantoux (PPD) tuberculin skin test or a positive Interferon Gamma Release Assay during screening or within 12 weeks prior to screening. The following are acceptable assays: QuantiFERON[®] - TB Gold test (QFT-G), QuantiFERON[®] - TB Gold In-Tube test (QFT-GIT) and T-SPOT[®] - TB test during screening or within 12 weeks prior to screening.
- A positive Mantoux tuberculin skin test is defined as ≥ 5 mm of induration (or as defined by country specific or local standards) at 48-72 hours without consideration of prior Bacillus Calmette-Guerin (BCG) vaccination. Documentation of the dose and product used for the Mantoux tuberculin test as well as the official test reading must be obtained and available in the subject's source documentation.
 - An Interferon-Gamma Release Assay (IGRA) is preferred for subjects with a prior BCG vaccination, but may be used for any subject. Documentation of IGRA product used and the test result must be in the subject's source documentation.
 - If the results of the IGRA are indeterminate, the test may be repeated, and if a negative result is obtained, enrollment may proceed. A positive test on repeat is exclusionary.
13. Current routine household contact with children or anyone else who have received varicella or oral polio or any other live (attenuated) vaccine within 6 weeks of first study dose, or during the course of the study (including the Follow Up period).
14. Any live (attenuated) vaccines from 30 days prior to the Baseline Visit and through the Follow Up Visit.

15. Subjects who have been in contact with people with acute infections within 2 weeks prior to the Screening Visit or in the period between the Screening Visit and the Baseline Visit.
16. History of any lymphoproliferative disorder (such as Epstein-Barr Virus (EBV)-related lymphoproliferative disorder, as reported in some subjects on immunosuppressive drugs), history of lymphoma, leukemia, myeloproliferative disorders, multiple myeloma, or signs and symptoms suggestive of current lymphatic disease.
17. Have a history of a major organ transplant (eg, heart, lung, kidney and liver) or hematopoietic stem cell/marrow transplant. Skin grafts are allowed.
18. History of severe allergic or anaphylactoid reaction to kinase inhibitors, or corticosteroid preparations.
19. Subjects with malignancy or history of malignancy (including but not limited to lymphoma, leukemia, or lymphoproliferative disease), with the exception of subjects with adequately treated or excised non-metastatic basal cell or squamous cell cancer of the skin or cervical carcinoma in situ.
20. Pre-existing chronic autoimmune disease (eg, inflammatory bowel disease, Systemic Lupus Erythematosus (SLE), moderate to severe atopic dermatitis) other than RA. Secondary Sjogren's -Syndrome associated with RA may be included.
21. Major surgery within 4 weeks of the Screening Visit or if scheduled to occur during the study, excluding diagnostic surgical procedures.
22. Previous treatment with total lymphoid irradiation.
23. Subjects with any condition possibly affecting oral drug absorption (eg, gastrectomy, clinically-significant diabetic gastroenteropathy, or certain types of bariatric surgery such as gastric bypass). Procedures such as gastric banding that simply divide the stomach into separate chambers are not exclusionary.
24. Screening 12-lead ECG that demonstrates clinically relevant abnormalities (eg, QTc >450 msec or a QRS interval >120 msec) which may affect subjects' safety or interpretation of study results. If QTc exceeds 450 msec, or QRS exceeds 120 msec, the ECG should be repeated two more times and the average of the three QTc or QRS values should be used to determine the subject's eligibility.
25. Have current or recent history of clinically significant severe or progressive hearing loss or auditory disease. Subjects with hearing aids will be allowed to enter the study provided their hearing impairment is considered controlled/clinically stable.
26. Subjects with an oral or tympanic temperature at the Baseline Visit of 38°C or higher.

27. Presence of any of the following laboratory abnormalities at the Screening Visit or within the 3 months prior to first study dose:
- Alanine aminotransferase (ALT) and aspartate aminotransferase (AST) levels ≥ 1.5 times the upper limit of normal (ULN).
 - Total bilirubin level ≥ 1.5 times the ULN; subjects with a history of Gilbert's syndrome may have a direct bilirubin measured and would be eligible for this study provided the direct bilirubin is \leq ULN and other liver function assessments are normal.
 - Hemoglobin level ≤ 90 g/L (9.0 g/dL).
 - Platelet count $\leq 100 \times 10^9/L$ (100,000 cells/mm³) or $\geq 1000 \times 10^9/L$ (1,000,000 cells/mm³).
 - White blood cell (WBC) count $\leq 3.0 \times 10^9/L$ (3000 cells/mm³) or absolute neutrophil count (ANC) < 1500 cells/mm³ or absolute lymphocyte count of $< 0.5 \times 10^9/L$ (< 500 cells/mm³).
 - Serum creatinine level ≥ 177 $\mu\text{mol/L}$ (2 mg/dL).
 - Glycosylated hemoglobin (HbA1C) $> 10\%$.
28. In the opinion of the investigator or sponsor, have any uncontrolled clinically significant laboratory abnormality that would affect interpretation of study data or the subject's participation in the study.
29. Grade 3 or greater laboratory abnormality based on the Common Terminology Criteria for Adverse Events (CTCAE) version 4.03 toxicity scale.

Screening laboratory tests with abnormal results may be repeated once to confirm abnormal results. If results return to normal protocol acceptable limits within the 5-week screening period, the subject may enter the study.

Subjects who fail screening can be rescreened once.

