Laboratory Evaluations										
Blood Chemistry ^h	X	X			X		X		X	X
Hematology	X	X	X	X	X	X	X		X	X
Rheumatoid Factor (RF)	X	X			X		X		X	X
C-Reactive Protein (hsCRP)	X	X	X	X	X	X	X		X	X

Protocol Activity	Screening	Treatment Period						Follow Up/End of Study		Early Withdrawal ^b
		1	2	3	4	5	6	7	8 ^s	
Visit Identifier		Week 0	Week 1	Week 2	Week 4	Week 6	Week 8	Week 10	Week 12	
Week ^a		Day 1 ^a	Day 8	Day 15	Day 29	Day 43	Day 57	Day 71	Day 85	
Study Day	Days -35 to Day 0	Day 1 ^a	Day 8	Day 15	Day 29	Day 43	Day 57	Day 71	Day 85	
Visit Window		±2 Days based on Week 0/Day 1 visit								
Anti CCP Antibodies (ACPA)	X	X			X		X		X	X
Erythrocyte Sedimentation Rate (ESR)		X	X	X	X	X	X		X	X
Serum Ig (IgA, IgM, IgG)		X					X			X
Serum IgE		X					X			X
Sample for IP-10		X					X		X	X
Urinalysis	X	X	X	X	X	X	X		X	X
Pregnancy test ^l	X	X	X	X	X	X	X		X	X
FSH test (if applicable) ^l	X									
HBsAg, HBcAb, HBsAb and HCVAb antibody ^j	X									
HIV testing ^k	X									
HbA1c	X									
Tuberculosis test ^l	X									
Viral Surveillance ^u	X	X	X	X	X	X	X		X	X
Sample for flow cytometry		X					X		X	
Banked RNA biospecimen (Prep R1) ^m	X	X					X		X	
Banked plasma biospecimens (Prep B1) ^m		X			X		X		X	
Banked serum biospecimens (Prep B2) ^m		X			X		X		X	
Genomic banked biospecimen (Prep D1) ^{q,m}		X								
Study Treatment										
Randomization (after all screening procedures are complete and reviewed)		X								
Administration and Dispensing of PF-06651600 or Placebo ^o		X	X	X	X	X	X			
Investigational Product Accountability			X	X	X	X	X			X

Protocol Activity	Screening	Treatment Period						Follow Up/End of Study		Early Withdrawal ^b
	1	2	3	4	5	6	7	8 ^s	9	
Visit Identifier	Week ^a	Study Day	Week 0	Week 1	Week 2	Week 4	Week 6	Week 8	Week 10	Week 12
Visit Window	Days -35 to Day 0	Day 1 ^a	Day 8	Day 15	Day 29	Day 43	Day 57	Day 71	Day 85	
Review of subject diary (review of subjects dosing record), IP accountability and compliance check throughout the study ^p			X	X	X	X	X	X		X
Pharmacokinetic										
Pre-dose (0hr) blood sample for PK analysis of PF-06651600			X	X	X	X	X	X		X ^w
Blood sample for PK analysis of PF-06651600 (0.5 hr) post dose					X	X	X	X		
Blood sample for PK analysis of PF-06651600 at 1 hr post dose					X		X	X		
Blood sample for PK analysis of PF-06651600 at 2 and 4 hr post dose								X		
Efficacy assessments										
Tender/Painful Joint Count (68)	X	X	X	X	X	X	X	X	X	X
Swollen Joint Count (66)	X	X	X	X	X	X	X	X	X	X

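### Exclusion 10(g) lets a subject positive only for hepatitis B core antibody enter without an HBV DNA result

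*Protocol*

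**What the plan says.** Protocol Section 4.2, item 10(g), sets out hepatitis B screening in three steps. HBsAg-positive subjects are out. Subjects who are HBsAg-negative and HBcAb-positive "must have further testing for hepatitis B surface antibody (HBsAb"). The only consequence attached to that test is: "If HBsAb is positive, the subject will be excluded from the study".

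Item 10(h), directly below, covers hepatitis C. A positive HCV antibody triggers a reflex HCV RNA test, and "Only subjects with negative HCV Ab or HCV RNA will be allowed to enroll in the study".

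The Schedule of Activities lists "HBsAg, HBcAb, HBsAb and HCVAb antibody" at screening only and refers back to Section 4. Table 6 (Section 7.2.1) includes HCV RNA but not HBV DNA. Neither the protocol nor the SAP names HBV DNA anywhere.

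**The concern.** 10(g) does not accept a negative HBsAg as sufficient once core antibody is present; it asks for another test. It then gives a consequence for one of the two possible results. In a list of exclusions, a subject who meets none is eligible, so the HBsAb-negative subject passes.

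The wording has three possible explanations: the word for a positive result may have been written where a negative was meant, a second sentence may be missing, or the rule may be as intended. The documents do not say which.

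What is at stake is subject safety. The Introduction describes JAK3 as a target for immune suppression. The drug is given daily for 8 weeks on top of required methotrexate, with prednisone up to 10 mg per day or equivalent allowed (Section 3). A subject whose hepatitis B status the protocol itself flags for further testing could begin this regimen with no virological check.

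**Working it through.** No plan figure has to be reproduced, because the point is one of eligibility logic. The check enumerates the outcomes, looks for another rule that closes the gap, and then reads the on-treatment schedule.

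**1. Outcomes under 10(g) and 10(h)**

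| Screening result | Outcome as written | Viral nucleic acid test required |
|---|---|---|
| HBsAg+ | Excluded | None |
| HBsAg−, HBcAb− | Not excluded | None |
| HBsAg−, HBcAb+, HBsAb+ | Excluded | None |
| HBsAg−, HBcAb+, HBsAb− | Not excluded; no outcome stated | None |
| HCV Ab+, HCV RNA+ | Excluded | HCV RNA |
| HCV Ab+, HCV RNA− | Allowed | HCV RNA |

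Of the two HBsAb results that 10(g) can produce, one has a stated outcome. HBV DNA results required before the first dose: 0. The indeterminate-IGRA rule in exclusion 12 is also a follow-up-test rule, and it states both results of the repeat test.

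**2. Other rules that might catch this subject**

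- 10(c) covers "Known active or history of recurrent bacterial, viral, fungal, mycobacterial or other infections". It needs a known active or recurrent infection.
- Exclusion 27 is a fixed limit on "Alanine aminotransferase (ALT) and aspartate aminotransferase (AST) levels" and on total bilirubin, at 1.5 times the upper limit of normal. It is a liver-function test, not a virological one.
- Exclusion 3 refers to a "laboratory abnormality that may increase the risk associated with study participation" and exclusion 28 to subjects who "have any uncontrolled clinically significant laboratory abnormality". These, and exclusion 4, depend on judgment.
- Viral surveillance (Section 7.2.10; Table 6 footnote e) is exploratory and does not name HBV. The footnote's list is open-ended, so HBV testing is permitted but not required. Results may come late, so it cannot serve as an entry test.

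These rules may remove some core-antibody-only subjects. None excludes on that status or requires a virological result.

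**3. Scheduled checks after the first dose** (Schedule of Activities and Table 6)

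- Treatment visits after Day 1: Days 8, 15, 29, 43 and 57, so 5.
- Blood chemistry, which holds AST/ALT and total bilirubin: Days 29 and 57, so 2 of 5.
- Hematology (which includes PT/INR) and urinalysis (which includes urine bilirubin): 5 of 5. Neither tests for HBV.
- First post-dose AST/ALT: 29 − 1 = 28 days after Day 1. With the ±2-day window, 27 − 1 = 26 to 31 − 1 = 30 days.
- Interval to the next: 57 − 29 = 28 days. With the window, 55 − 31 = 24 to 59 − 27 = 32 days.

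Hepatitis B testing is named again only in the work-up of a liver signal (Section 8.4.2 and Appendix 5, footnote a).

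**The case against.** The strongest reply concerns severity. The documents give no rate for core-antibody-only status, for viraemia in such subjects, or for reactivation on this drug, and nobody in the trial may be affected. That stands, and the risk is not quantified here. What the documents do show is that 10(g) treats core antibody as a reason for further testing and then lets one result through with nothing more.

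A second reply is that exclusion lists need not state who is eligible; 10(f) says nothing about HIV-negative subjects either. That is fair as a matter of form, and it confirms the reading: the HBsAb-negative subject is admitted by default. The difference is that an HIV-negative subject has no finding to resolve, whereas this one does.

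A third is that on-treatment protection is better than the AST/ALT schedule alone suggests. Chemistry is also drawn at Day 1, Week 12 and early withdrawal, and unscheduled tests are allowed. Appendix 5 requires a re-test within 1 week for any AST or ALT at or above 3 times the upper limit of normal, and discontinuation after two sequential elevations at set thresholds. Targeted examinations and adverse event collection continue throughout. All true, and this limits harm once a liver signal appears. None of it governs entry.

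Finally, if the direction of the HBsAb rule was inverted by mistake, excluding every HBcAb-positive subject would also bar a group the sponsor meant to admit. That stands, and it is why the fix offers a second route.

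**Conclusion.** The concern holds. Followed as written, 10(g) admits the HBsAg-negative, HBcAb-positive, HBsAb-negative subject with no HBV DNA result, while the adjacent hepatitis C rule requires viral RNA to be negative in the parallel case. The wording needs correction if it is inverted or incomplete. If it is deliberate, it admits a group flagged for more testing without a virological check.

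The conclusion rests on the literal text and on the absence of any visible HBV DNA requirement; it does not depend on knowing the sponsor's intent. The number of subjects exposed cannot be estimated from the documents and may be zero. Sample size, power and type I error are unaffected. It is nevertheless a must-fix safety item, because exposure cannot be undone after the first dose and the correction is small.

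**What to change.** Amend 10(g) to read: *Subjects positive for HBsAg or HBcAb will be excluded.* Because the current text already excludes HBcAb-positive, HBsAb-positive subjects, this adds only the core-antibody-only group and leaves no result without an outcome. The cost is one sentence and some extra screen failures, whose number the documents do not allow one to estimate.

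If the sponsor prefers to admit any HBcAb-positive subjects, 10(g) should state the outcome separately for HBsAb-positive and HBsAb-negative. It should also require a negative HBV DNA within the screening period of up to 35 days and before the first dose, parallel to 10(h). List the test in Table 6 and the Schedule of Activities, and run it as a clinical laboratory test, since viral-surveillance results may be delayed. The cost is one assay per HBcAb-positive subject considered for entry, with no added visit. HBV DNA monitoring during treatment would be optional.
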